12.0 Secondary Endpoint Analyses

There are no secondary endpoints for the study.

13.0 Sample Size and Power for Primary Endpoints

13.1 Group A Primary Endpoint – Anesthesia Effectiveness

[REDACTED]

[REDACTED]

[REDACTED]

Twenty-four evaluable subjects in Group A will provide >95% power to detect the assumed mean difference in mean pain scores between Sham and Treatment. In order to account for uncertainty about the effect size, a total sample size of 40 is planned. Assuming 10% attrition (screen failure or withdrawn) in Group A, a sample size of 44 subjects is expected to yield an evaluable sample size of 40.

13.2 Group B Primary Endpoint – Tube Placement Tolerability

[REDACTED]

[REDACTED]

A sample size of 30 evaluable subjects in Group B will provide greater than 95% power at the one-sided 2.5% significance level for a non-parametric bootstrap test of the mean VAS score against a performance goal of 4.5.

14.0 Safety Endpoint Analyses

14.1 Adverse Events

Adverse events (AEs) reported during the study will be coded using the Medical Dictionary for Regulatory Activities (MedDRA). The number and percentage of subjects reporting adverse events will be summarized by MedDRA system organ class and preferred term for each Group (A and B).

The frequency of each event will be summarized by seriousness, severity and by relationship to the study device, procedure and/or drug. For all AE tables, a subject reporting the same AE more than once will be counted once when calculating the number and percentage of subjects with that particular event. If a subject reports the same AE more than once or has the same AE on multiple occasions, the maximum severity grade recorded for the event will be presented.

Overall summaries of serious and non-serious AEs will be presented. The overall summaries will include the number and percentage of patients experiencing AEs classified by treatment, relationship to device/procedure/study drug, MedDRA SOC (System Organ Class) and preferred term. Summaries of AEs will also be presented by severity for each treatment group including the number and percentage of patients

experiencing AEs classified by relationship to device/procedure/study drug, SOC and preferred term.

Safety events will be reported for all subjects in which the lidocaine solution was introduced into the ear (Safety Analysis Set) and will be reported for the following time intervals:

- Events occurring during the procedure visit
- Events occurring between the procedure through the subject's final follow-up visit

[REDACTED]

[REDACTED]

Complete patient listings of all AEs will be provided. For each AE the following will be specified: start and stop dates, severity grade and MedDRA SOC, relationship to study device, relationship to procedure, relationship to study drug, action taken, outcome of the adverse event and seriousness, where appropriate. Any unanticipated adverse events will be noted.

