The two technologies consist of a Tube Delivery System (TDS) and an Iontophoresis System (IPS). The TDS is a mechanical device that rapidly performs a myringotomy and delivers a preloaded tympanostomy tube with single-button actuation. The IPS is a single-use microprocessor-controlled direct current (DC) generator used prior to the TDS to facilitate anesthesia of the tympanic membrane by driving ions of a drug solution into the tissue.

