Group B subjects will receive active lidocaine iontophoresis and TDS-mediated tube placement in all ears that require tube insertion. The VAS score will be collected *after* any manipulations required to place the tube so that the pain score fully reflects the activities required to place the tube. VAS score will be collected for each ear undergoing tube placement. If a subject discontinues iontophoresis or the procedure prior to tube placement with the TDS, a VAS score will be collected for the attempted procedure. The pain score will be compared to a fixed performance goal.

Vital signs (diastolic and systolic blood pressure, heart rate, respiratory rate and pulse oximetry) will be monitored 15 minutes and immediately prior to iontophoresis, immediately following the iontophoresis, following tube placement, 30 minutes and 60 minutes after completion of iontophoresis for all Group B subjects.

A follow-up at 3 weeks is required for all subjects, at which point an otologic examination, cranial nerve exam, tympanometry and audiometry will be conducted.

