13.0 ASSESSMENT OF SAFETY

13.1. Adverse Events

All reported or observed adverse events that occur during or after the procedure will be recorded. The study Investigator will determine whether an adverse event has occurred, whether life-threatening, serious or non-serious. Pre-existing conditions should not be reported as adverse events unless there has been a worsening in the severity or frequency,

which cannot be attributed to natural history or progression of the disease. This definition does not depend on the causal relationship with the device, drug or protocol requirements.

Any change of clinical significance, including vertigo, nausea and vomiting, derived from the protocol evaluations including observations and patient-reported findings will be included as adverse events. Changes in vital signs 30% or greater compared to baseline will be considered adverse events.

All Adverse Events (AEs) will be recorded on dedicated AE case report forms. The event, date of onset, severity, seriousness, duration, treatment, outcome, date or resolution and relationship to device, procedure or drug will be recorded on the AE case report form (CRF). AEs will be categorized by seriousness, relatedness to procedure, investigational drug, or device whether anticipated or unanticipated. All adverse events will be coded using standard terms.

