13.4. Adverse Event Classification***Adverse Event Severity***

All adverse events will be classified as to the severity of the event based on the definitions consistent with AE severity grading scale provided by the National Cancer Institute, of the NIH and US Department of Health and Human Services – Common Terminology Criteria

for Adverse Events v.4.03 (CTCAE) June 14, 2010 (**Table 4**).⁴⁵ Grade level of adverse event refers to the severity of the event.

Table 4. Table of Adverse Event Severity

AE Severity	Definition
Grade 1 – Mild	Asymptomatic or mild symptoms; clinical or diagnostic observations only; intervention not indicated.
Grade 2 – Moderate	Minimal, local or non-invasive intervention indicated; limiting normal daily activities
Grade 3 – Severe	Severe or medically significant but not immediately life threatening; hospitalization or prolongation of hospitalization indicated; disabling limiting self-care
Grade 4 – Life Threatening	Life threatening consequences; urgent intervention indicated
Grade 5 – Death	Death related to adverse event

Any increase in the severity of an AE should be documented.

Adverse Event Causality

Causality regarding device, drug and/or procedure relationship will be assigned by the Investigator to all adverse events according to the definitions provided in **Table 5**.

Table 5. Table of Adverse Event Causality

Causality	Description*
Certain	A clinical event, including laboratory test abnormality, occurring in a plausible time relationship to procedure, device or drug administration/exposure, which cannot be explained by concurrent disease, other interventions or other drugs and considered definitely related to the study drug, device or procedure.
Probable	A clinical event, including laboratory test abnormality, with a reasonable time sequence to procedure, device or drug administration/exposure, unlikely to be attributed to concurrent disease, other interventions or drugs.
Possible	A clinical event, including laboratory test abnormality, with a reasonable time sequence to procedure, device or drug administration/exposure, but which could also be explained by concurrent disease, other interventions or drugs.

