13.6. Device Malfunctions

Any inadequacy of the device or packaging with respect to its identity or performance will be recorded as a device malfunction. Information regarding the device identity (eg, device name/code and lot number), temporal aspect of the malfunction (eg, prior to opening,

during preparation during procedure), nature of the malfunction and relatedness to potential adverse events will be collected on appropriate CRFs.

[REDACTED]

[REDACTED]

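### Adverse event causality uses one undivided device category, so the tube delivery system's own event rate in Group B cannot be derived from the planned tables

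*SAP*

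**What the plan says.** Protocol 6.2 describes two separate technologies, the IPS and the TDS. Group B gets both: "Group B subjects will receive active lidocaine iontophoresis and TDS-mediated tube placement in all ears that require tube insertion" (Protocol 11.2). Protocol Table 3 puts the whole sequence in one procedure visit.

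The visible text treats causality the same way in four places:

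- **Form content, Protocol 13.1:** "relationship to device, procedure or drug will be recorded on the AE case report form (CRF").
- **Assignment rule, Protocol 13.4:** "Causality regarding device, drug and/or procedure relationship will be assigned by the Investigator to all adverse events".
- **Tables, SAP 14.1:** "The frequency of each event will be summarized by seriousness, severity and by relationship to the study device, procedure and/or drug".
- **Listings, SAP 14.1:** "relationship to study device, relationship to procedure, relationship to study drug".

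On the denominator, SAP 14.1 says: "Safety events will be reported for all subjects in which the lidocaine solution was introduced into the ear (Safety Analysis Set"). SAP 7.2.3 sets the Group B Safety Analysis Set equal to the FAS, and entry does not depend on TDS use. Protocol 11.2 provides for subjects who stop iontophoresis or the procedure before the TDS is used. They have already had lidocaine instilled, so they stay in the set.

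Device identity is requested for malfunctions (Protocol 13.6). The visible text has no equivalent for adverse events.

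**The concern.** The two devices carry different hazards. The IPS is an adhesive earplug, a current source and a skin electrode; the TDS cuts the tympanic membrane and leaves a tube in it. In Group B, an ear canal abrasion, a tympanic membrane bleed or otalgia rated device-related could come from either. With one category, the planned table adds the two sources together.

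Objective 2 (SAP 2.0) concerns the tolerability and safety of tube placement after local anesthesia, and adverse event occurrence is the only safety endpoint (SAP 3.2). A reader of the final report will want to know how often the TDS or its tube caused harm. The planned output does not give that numerator, and the planned denominator includes subjects who were never exposed to the TDS.

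**Working it through.** The documents state no adverse event rate, so there is no plan figure to reproduce. The check compares provisions and then illustrates the effect with assumed counts.

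**Step 1. Which device rates can be derived?**

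| | IPS | TDS/tube |
|---|---|---|
| Exposed subjects | Everyone instilled, because the drug goes in through the Earset (Protocol 12.5.5) | Only those who reach tube placement |
| Is the Safety Analysis Set the exposed group? | Yes | No, if anyone stops early |
| Data on that device alone | Group A (Protocol 11.2), with events by treatment group (Protocol 14.3.4) | None |
| Attributed numerator in Group B | Not in the visible text | Not in the visible text |

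**Step 2. Can the split be recovered another way?**

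- *Timing.* Both devices are used at one visit. The SAP intervals are the procedure visit, and procedure through final follow-up. Dates are recorded (Protocol 13.1, SAP 14.1), and no clock time is listed.
- *The procedure category.* It is also undivided, although Group B undergoes both iontophoresis and tube placement.
- *Subtracting Group A.* Group A is healthy volunteers aged 18 to 50, treated in one ear, half of them without current. The groups are not randomized against each other, so a difference would not isolate the TDS.
- *Return-electrode erythema (SAP 14.3).* It is specific to the IPS but says nothing about canal or tympanic membrane events.

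**Step 3. Numerator, illustrated.** Assume 30 subjects exposed to both devices and 6 with a device-related event, each due to one device. Let k be the number due to the TDS:

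- TDS rate = k/30, IPS rate = (6 − k)/30, with k from 0 to 6.
- k = 0: TDS 0/30 = 0%, IPS 6/30 = 20.0%.
- k = 6: TDS 6/30 = 20.0% (exact 95% CI 7.7% to 38.6%), IPS 0%.

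The planned table would look the same in every case.

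**Step 4. Denominator, illustrated.** Assume 3 subjects with a TDS-related event among 30 exposed: 3/30 = 10.0% (exact 95% CI 2.1% to 26.5%). On the Safety Analysis Set the reported figure is 3/N:

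| Instilled, N | Reported rate |
|---|---|
| 30 | 10.0% |
| 32 | 9.4% |
| 34 | 8.8% |
| 41 | 7.3% |
| 45 | 6.7% |

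The last two rows are extremes. They come from the cap of 85 less 44 Group A subjects (SAP 13.1), 85 − 44 = 41, or less 40 evaluable ones, 85 − 40 = 45. The cap counts consented subjects (Protocol 11.4.1) and allows about 15 for screen failures and withdrawals (Protocol 11.4). Screen failures receive no lidocaine, so the true N should be lower.

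In these illustrations the missing attribution matters more than the dilution.

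**The case against.** Four arguments go against the point.

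*The IPS rate is available.* A reader might infer that neither device's rate can be derived. The documents do not support that. The Safety Analysis Set is the IPS-exposed population, and Group A gives IPS-only events, though in healthy volunteers. This argument stands and confines the point to the TDS/tube rate and to attribution within Group B.

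*Some of the text cannot be seen.* Protocol 14.4.3 (Group B safety analysis) appears in the contents, but its body is not visible. Part of SAP 14.1 is blacked out, and the adverse event form is not supplied. The form may already separate the devices. This stands as a caveat. Still, the visible description of the form's content and the itemized listing fields both name one device relationship, and a hidden table could not split events by an attribution that was not collected.

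*Other data help.* The canal and tympanic membrane are inspected under the microscope after iontophoresis and before tube placement (Protocol 12.5.9). Vital signs are taken after each step (Protocol 12.2.10). Malfunction records link to adverse events (Protocol 13.6), and full listings allow case review of about 30 subjects. Procedure data (SAP 10.0) may give the TDS-exposed count. This stands in part: the investigator is often able to judge the source. That favors recording the judgment when the event occurs, since later reconstruction is weaker. Most device harms also need no malfunction.

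*Per-device rates are not a stated objective.* Objective 2 covers the combined sequence, and no safety hypothesis is tested. This is true and limits the weight of the point, but the plan already chooses to tabulate events by relationship to device.

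**Conclusion.** The concern holds in a limited form. On the visible text, Group B device-related events cannot be assigned to the TDS/tube from the planned tables, and no TDS-exposed denominator is defined, so a TDS-related rate would be diluted by anyone who stops early. The IPS denominator is right as planned.

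The size is unknown. The counts of 30 exposed, 3 or 6 with events, and 30 to 45 instilled are assumptions chosen to show the mechanism. A reader might take the 41 or 45 case as the expected dilution, but the documents give no basis for that, and with no early stops the dilution is zero. The conclusion also assumes that the unseen form and the redacted text do not already separate the devices. Neither primary test is affected. This is an inexpensive improvement to safety reporting.

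**What to change.** On the adverse event form, and in the SAP 14.1 tables and listings, replace the single device relationship with two: relationship to the IPS and relationship to the TDS/tube, with both allowed for one event. For Group B, report TDS/tube-related events also as a percentage of subjects in whom TDS placement was attempted, beside the Safety Analysis Set percentage. If the form already separates the devices, only the SAP wording and tables need to change.

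The cost is a few tick boxes, one extra percentage column and a definition of attempted TDS placement. Treatment, sample size and the primary analyses do not change. Some events will be attributed to both devices because the investigator cannot tell them apart, and with about 30 subjects many cells will be sparse. For that reason a finer split, for example dividing the procedure category as well, is more than this study needs.

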14.2 Vital Signs

Descriptive statistics of mean, SD, minimum, and maximum will be presented for vital signs measurements (systolic blood pressure, diastolic blood pressure, heart rate, respiratory rate, blood oxygen saturation) at all protocol-defined time points. Mean and median change from baseline to post-iontophoresis time point for each vital sign will be presented for the three protocol-defined post-iontophoresis time points (0, 30 and 60 minutes post) by treatment group. Any clinically significant change in vital sign measurements (30% or greater change from baseline) will be reported as an adverse event.

14.3 Erythema Assessment at Return Electrode Location

Erythema observed for the skin under the return electrode will be assessed by the treating physician and categorized by grade level (0 through 4) prior to and immediately after iontophoresis. Erythema findings will be summarized by number

and proportion of subjects in the Safety Analysis Set for each erythema grade level for each Group. Number and proportion of subjects reporting discomfort at the return electrode location will be summarized.

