5.0 Study Cohorts

There are two cohorts in the study:

Group A: Healthy adult volunteers randomized to active lidocaine iontophoresis or sham lidocaine iontophoresis, followed by assessment of anesthesia effectiveness.

Group B: Adults indicated for tympanostomy tube placement undergoing lidocaine iontophoresis and TDS-mediated tympanostomy tube placement, followed by assessment of tube placement tolerability.

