10.0 Procedure Characteristics and Device Malfunctions

Procedure and device performance characteristics will be summarized using descriptive statistics for each Group, and by treatment for Group A only.

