14.4 Audiometric Assessments

Change in audiometric measurements (shifts) from baseline to each follow-up visit for subjects in the Safety Analysis Set will be presented using descriptive statistics (mean, SD, median, minimum and maximum). Shifts in air conduction (AC) and bone conduction (BC) hearing thresholds will be reported for each frequency (500, 1000, 2000 and 4000 Hz) on a by-ear basis, and for each treatment arm in Group A (active or sham treatment). Shifts from baseline to each follow-up visit in air-bone gap (air conduction minus bone conduction) will also be reported for each frequency (500, 1000, 2000 and 4000 Hz) on a by-ear basis, and for each treatment arm in Group A. Shifts in air conduction pure tone average (AC PTA), bone conduction PTA (BCA) and air-bone gap averages will be presented for each follow-up time point by ear for each Group and by treatment. For all PTA measurements, the PTA will be calculated by adding the threshold levels in decibels (dB) obtained at each frequency tested divided by number of frequencies tested.

Shift tables for air conduction pure tone averages greater than 15 dB (>15dB) by ear will be calculated, and presented by ear for each Group and by treatment for each follow-up time point.

Degree of hearing loss severity will be defined according to the protocol (slight through profound) and presented by subject for each Group and by relationship to study device, procedure or study drug.

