14.5 Tympanometry

Tympanometry results are used to assess of tube patency (for Group B only) and for changes in middle ear condition. Tympanometry will be performed for both ears for all subjects (Groups A and B) at screening and at all follow-up visits. The number and percentage of ears in each Group with tympanogram types A, B or C will be presented for all subjects and for each treatment arm (sham or active treatment in Group A) in the Safety Analysis Set at screening and all follow-up time points.

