14.6 Otoscopic Assessments

Otoscopic examination will be performed in all ears intended for treatment at all protocol-defined time points. The number and percentage of ears in each Group with abnormal findings for the external acoustic meatus or tympanic membrane will be presented for all subjects in the Safety Analysis set for screening and all follow-up time points.

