14.7 Cranial Nerve Function

Cranial nerve function physical examination will be performed for all subjects at screening, post-procedure and at all follow-up visits. The change from baseline for subjects in the Safety Analysis set in each Group will be presented for all follow-up visits.

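### SAP 14.3, 14.6 and 14.7 specify no active-versus-sham breakdown for Group A, so local findings below the adverse-event threshold would not be compared between arms

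*SAP*

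**What the plan says.** SAP 5.0 defines the first cohort as "Group A: Healthy adult volunteers randomized to active lidocaine iontophoresis or sham lidocaine iontophoresis", so the word Group, used alone, covers both arms of Group A.

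Three safety sections summarize at that level and go no further:

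- **SAP 14.3, erythema:** the number "and proportion of subjects in the Safety Analysis Set for each erythema grade level for each Group".
- **SAP 14.6, otoscopy:** "The number and percentage of ears in each Group with abnormal findings for the external acoustic meatus or tympanic membrane", at screening and at follow-up.
- **SAP 14.7, cranial nerves:** "The change from baseline for subjects in the Safety Analysis set in each Group will be presented for all follow-up visits".

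SAP 14.3 also covers discomfort under the patch, with no level of summary at all: "Number and proportion of subjects reporting discomfort at the return electrode location will be summarized".

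Other sections do name the arm. Procedure and device characteristics (SAP 10.0) are "summarized using descriptive statistics for each Group, and by treatment for Group A only". Audiometric shifts (SAP 14.4) are reported by ear "and for each treatment arm in Group A (active or sham treatment"). Tympanogram types (SAP 14.5) are counted within each Group and then, in addition, "for each treatment arm (sham or active treatment in Group A").

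**The concern.** The two arms of Group A are planned to differ in one respect only. The sham channel is not activated, while the drug solution, Earset and return patch are the same (SAP 4.0; Protocol 12.5.5 and 12.5.6). An active-versus-sham comparison therefore isolates the effect of the current from that of the patch adhesive, the ear plug and the drug. Group B has no sham arm and cannot supply this.

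The point bears most directly on the skin under the return electrode. The protocol's list of device safety features (Protocol 7.1.1) ties skin irritation there to current density. Erythema at the site is scored before and after iontophoresis (Protocol 12.5.5 and 12.5.7). A single Group A line would mix roughly equal numbers of subjects with and without current, and a reader could not tell whether a mild reaction came from the current or from the patch.

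At stake is the interpretation of descriptive local safety data. No hypothesis test is involved.

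**Working it through.** The plan states no figure on this point, so there is none to reproduce. The check is a comparison of sections, followed by a short illustration.

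**Step 1. Level of summary by section.**

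| SAP section | Content | By Group | By arm in Group A |
|---|---|---|---|
| 10.0 | Procedure and device performance | yes | yes |
| 14.1 | Adverse events | yes | yes (by treatment) |
| 14.4 | Audiometry | yes | yes |
| 14.5 | Tympanometry | yes | yes |
| 14.3 | Erythema grade | yes | not stated |
| 14.3 | Electrode discomfort | not stated | not stated |
| 14.6 | Otoscopy | yes | not stated |
| 14.7 | Cranial nerves | yes | not stated |

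SAP 14.5 settles the reading. It refers to each Group and then adds the arms as a separate item, so in this SAP the reference to Group does not by itself imply an arm split.

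**Step 2. What reaches a by-arm table by another route.** Adverse events are broken down by treatment (Protocol 14.3.4; SAP 14.1). A Draize score of 3 or more is an adverse event (Protocol 12.5.7), as is any clinically significant change found at a protocol evaluation (Protocol 13.1). What remains without a specified comparison is:

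- erythema of grade 0, 1 or 2;
- return-electrode discomfort, for which no grouping is given;
- otoscopic and cranial nerve findings not reported as adverse events.

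**Step 3. What pooling loses.** The inputs are 40 evaluable subjects and 1:1 allocation (SAP 4.0 and 6.0), so 40 × 1/2 = 20 per arm. The documents give no expected rates, and the event counts below are assumed. With a events on active and s on sham, the pooled rate is (a + s)/40 and the difference is a/20 − s/20. The two-sided Fisher p-value only indicates how far apart the arms are; the plan has no such test. When s = 0 it equals 2 × C(20, a)/C(40, a). For a = 6 that is 2 × 38,760/3,838,380 = 0.020.

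| Active | Sham | Pooled | Difference | Fisher p |
|---|---|---|---|---|
| 2/20 | 0/20 | 2/40 = 5% | 10 points | 0.49 |
| 4/20 | 0/20 | 4/40 = 10% | 20 points | 0.11 |
| 6/20 | 0/20 | 6/40 = 15% | 30 points | 0.020 |
| 3/20 | 3/20 | 6/40 = 15% | 0 points | 1.0 |
| 8/20 | 0/20 | 8/40 = 20% | 40 points | 0.003 |

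The third and fourth rows are the point: the pooled entry is 6/40 in both, yet one split is a 30-point difference and the other is none. An effect that occurs only with current appears at half its rate in the pooled line.

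**The case against.** The strongest reply is that the plan already compares the arms where it matters. The only safety endpoint is the occurrence of adverse events, which are summarized by treatment and include marked erythema and clinically significant examination changes. The listings carry the Group A treatment for each subject (SAP 22.0). This stands, and it limits the point to findings below the adverse-event threshold. It does not remove the point, because erythema of grade 1 or 2 does not meet the Draize threshold and a listing is not a planned summary.

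A second reply is that no section says the arms will be combined. The three sections are silent on arm, and parts of the general statistical methods (Protocol 14.2), the Group A safety analysis (Protocol 14.3.4) and SAP 14.1 are blacked out. A general by-arm rule may sit there. That lowers confidence, but such a rule would make the arm wording in SAP 10.0, 14.4 and 14.5 redundant, and the visible general considerations in SAP 24.0 contain none.

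A reader might also infer three stronger things that the documents do not support:

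- **That exposed subjects are never shown on their own.** Every Group B subject receives active iontophoresis, so the Group B line is undiluted. It lacks only a control.
- **That new canal or membrane injury is hidden.** SAP 14.6 does show simple percentages at each visit, but a clinically significant injury is an adverse event. Eligibility also excludes otitis externa, damaged canal skin and perforated membranes in both Groups (Protocol 11.10).
- **That cranial nerve change is as closely tied to the current as erythema is.** Protocol 12.2.3 says only that the examination looks for potential adverse effects, so this is the weakest of the three sections.

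**Conclusion.** The point holds as a gap in descriptive reporting. As visibly written, SAP 14.3, 14.6 and 14.7 give no active-versus-sham breakdown, and SAP 14.3 gives no grouping for electrode discomfort. Sub-threshold findings would therefore not be set against sham, although that is the trial's only contrast that isolates the current. The case is strongest for erythema of grade 0 to 2 and electrode discomfort, weaker for otoscopy, and weakest for cranial nerves.

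It would be wrong to conclude that the sham control goes unused for local safety, since the adverse event tables do use it.

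The real size cannot be stated because the documents give no expected rates. The 6/40 example rests on assumed counts and on 20 subjects per arm. The conclusion also assumes that no blacked-out passage sets a general by-arm rule. The primary endpoints and power are unaffected.

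**What to change.** In SAP 14.3 (for both erythema grade and electrode discomfort), 14.6 and 14.7, add: *and by treatment arm (active, sham) for Group A*, in line with SAP 14.4 and 14.5. For electrode discomfort, state the Group level as well.

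Optionally, in SAP 14.6 also count treated ears that were normal at screening and abnormal at follow-up. This needs only the normal or abnormal classification already planned, and no grading of severity. In Group B such a table should be read knowing that a myringotomy and tube are expected at follow-up.

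The cost is a wording change and extra table columns. Arm, erythema grade and examination findings are already recorded, so no new data, visits or subjects are needed. If a blacked-out passage already requires summaries by arm, a cross-reference in each of the three sections is enough, together with a stated grouping for electrode discomfort.
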